2. At ~6am subjects are given a priming dose of [15N]-Phe (0.7 mg/kg), followed by continuous infusion over the next 8 hours of 15[N]-Phe (0.7 mg/kg).
3. 2H5-Phe infusion begins at time 0 and continues for 5hr at a variable rate to mimic meal 13C6-Phe Ra.
4. During the second phase of the study, CF patients will have been receiving insulin (basal or bolus) or placebo for 1 month. They will receive their usual insulin/placebo dose during the protein turnover study.
5. To calculate protein dynamics, free amino acids are extracted from plasma using acetic acid and analyzed as their t-butyldimethylsilyl ester derivatives. The molar percent excess (MPE) of phenylalanine isotopes will then be calculated above background

4.2. Drug/Device Handling: Study drug, insulin or placebo (insulin diluent) will be obtained from the manufacturer in standard insulin vials. The investigational pharmacy will cover the label so that the study medication will be blinded.

- IDS #4817

5. Procedures Involved

5.1. Study Design: This double-blind, placebo-controlled trial of insulin therapy in CF youth with abnormal glucose tolerance will assess the impact of 2 different insulin regimens on protein turnover. In Phase 1, stable isotope measurement of meal-stimulated protein flux will be done in CF patients and normal controls, followed by bi-weekly fasting blood draws x2 wks to assess individual proteins. In Phase 2, CF patients will receive once daily basal insulin, 3X daily rapid-acting insulin, or injectable placebo for 6 weeks. After the 1st month, the meal-stimulated protein flux study will be repeated, followed by bi-weekly fasting blood draws x2 wks to assess individual proteins. Power analysis suggests 15 patients are needed per group; 20 are planned to account for drop-outs due to acute illness and non-adherence (although we expect good adherence since the treatment period is short).

5.2. Study Procedures:

Phase 1: Baseline Assessment, No insulin therapy, All CF patients and controls will complete this phase

PROTOCOL TITLE: The Impact of Insulin Therapy on Protein Turnover in Pre-Diabetic Cystic Fibrosis Patients

VERSION DATE: 28 June 2021

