Randomized into group (once daily basal insulin, 3x daily rapid acting insulin, or placebo) Insulin (basal or rapid) or placebo, will be supplied by the manufacturer in identical standard insulin vials. Participants will be instructed in subcutaneous injection technique. Study medication adjustments will be made under the supervision of the research teams, who are quite familiar with insulin management in patients with CF, and who will be available at all times for support.

PROTOCOL TITLE: The Impact of Insulin Therapy on Protein Turnover in Pre-Diabetic Cystic Fibrosis Patients

VERSION DATE: 28 June 2021

Visit 3 (Week 6, +/- 7 days): Complete the meal-stimulated protein flux study part again from Phase 1 along with the DXA scan, CFQ-R, and CGM placement. There will not be a dietitian consult at this visit.

Visit 4 (Week 7, +/- 1 day): outpatient blood draw to assess individual proteins and removal of continuous glucose monitor

Visit 5 (Week 8, +/- 1 day): outpatient blood draw to assess individual proteins and end study.

Between Visits:

Study personnel will contact (e.g. telephone, email) patients every three days while insulin is being adjusted and weekly thereafter in addition to their study visits. During these contacts staff will review and adjust (if needed) the medication dose, review hypoglycemia symptoms and management, monitor acute illness or adverse events, provide education, and encourage adherence.

[figure not shown]
Participants will also be asked record their blood glucose levels at random times during the entire study. These need to be recorded to determine clinically if insulin adjustment is necessary.

Patients will receive all usual CF care; study participation will not impact standard-of-care treatment.

PROTOCOL TITLE: The Impact of Insulin Therapy on Protein Turnover in Pre-Diabetic Cystic Fibrosis Patients

VERSION DATE: 28 June 2021

5.3. Study Duration: Each study participant will be in the study for an 8 week duration.

- Anticipated duration to recruit all study participants is 4.5 years.
- The anticipated duration to complete all study procedures, including any long-term follow-up, and data analysis is 5 years.

5.4. Individually Identifiable Health Information: Research participants in this study will sign an Authorization to Use or Disclose Protected Health Information for Research Purposes.

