PROTOCOL TITLE: The Impact of Insulin Therapy on Protein Turnover in Pre-Diabetic Cystic Fibrosis Patients

VERSION DATE: 28 June 2021

8.3. Screening: Screening begins with identification of eligible subjects using the standard OGTT recommended annually for all CF patients. Currently at UMN we have 121 CF patients age 10-25, 58 of whom have IGT or INDET and meet study entrance criteria. Nine new patients per year in this age range are diagnosed with IGT or INDET at UM and thus become eligible for the study. An additional 46 non-diabetic children and youth age 10-25 years are followed at our Children's Hospitals and Clinics of Minnesota CF affiliate, 20 of whom currently have abnormal glucose tolerance. Three to four new patients per year become eligible. Our experience from previous CF studies in this age group suggests ~60% will agree to participate. Over the study period we anticipate that 45-50 CF patients will participate from UM and 10-15 from Children's. Normal control subjects will be recruited from fliers placed in the clinics and the University campus. In addition, siblings of CF participants will be invited to participate as controls. CF subjects will be randomized in a 1:1:1 ratio to basal insulin, pre-meal insulin, or injectable placebo (half 3x/daily pre-meal, half 1x/daily), stratified by 2 age intervals (10-17, 18-25y) and gender. Randomization will be done with computer-generated lists for each strata, in randomly alternating blocks of 3 and 6. The research subject, investigator and clinic personnel will be blinded to assignment. Healthy controls will be matched for gender, age and BMI percentile. The statistician will review control recruitment after every 5 subjects to ensure they are representative of the patient groups and determine whether specific control ages or genders should be recruited.

8.4. Vulnerable Populations:

- Children
- Pregnant women/Fetuses/Neonates
- Prisoners
- Adults lacking capacity to consent and/or adults with diminished capacity to consent, including, but not limited to, those with acute medical conditions, psychiatric disorders, neurologic disorders, developmental disorders, and behavioral disorders
- Approached for participation in research during a stressful situation such as emergency room setting, childbirth (labor), etc.
- Disadvantaged in the distribution of social goods and services such as income, housing, or healthcare

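### Blinding covers insulin versus placebo within an injection schedule, but not basal versus pre-meal insulin, so the unqualified blinding claim does not hold for Aim 2

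*Combined protocol and SAP*

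**What the plan says.** Section 5.1 describes the design: "This double-blind, placebo-controlled trial of insulin therapy in CF youth with abnormal glucose tolerance will assess the impact of 2 different insulin regimens". The regimens differ in frequency: "CF patients will receive once daily basal insulin, 3X daily rapid-acting insulin, or injectable placebo for 6 weeks". Section 8.3 gives the allocation, "CF subjects will be randomized in a 1:1:1 ratio to basal insulin, pre-meal insulin, or injectable placebo", and specifies the placebo as "injectable placebo (half 3x/daily pre-meal, half 1x/daily". It then says: "The research subject, investigator and clinic personnel will be blinded to assignment".

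The masking methods are in two places. Section 4.2: "The investigational pharmacy will cover the label so that the study medication will be blinded". Section 5.2: "Insulin (basal or rapid) or placebo, will be supplied by the manufacturer in identical standard insulin vials". No section describes dummy injections that would give every participant the same number of injections.

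Section 5.2 has the research team teach injection technique and review and adjust the dose at regular contacts. Section 4.1 says of the repeat flux study: "They will receive their usual insulin/placebo dose during the protein turnover study". Section 20.1 asks schools to oversee pre-meal dosing. Section 16.1 says the collaborators who model the mass-spectrometry data are blinded to arm.

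Section 14 analyses three groups, with placebo as one of them, by pairwise contrasts adjusted for baseline turnover. There is no term for injection schedule and no same-schedule comparison. The primary analysis is restricted to participants who took at least 70% of study medication. Rates of hypoglycemia and of non-adherence are compared between treatments.

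**The concern.** Covered labels and identical vials hide what is in the vial. They do not hide how often it is injected. Someone injecting once a day knows they are not on pre-meal insulin, and someone injecting three times a day knows they are not on basal. Aim 2 compares exactly those two regimens, so participants and schedule-aware staff know which side of that comparison each person could be on. The unqualified statement in section 8.3 is wrong for this comparison.

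Two things are at stake. First, Hypothesis 2 claims that basal insulin safely gives the same benefit. Its supporting comparisons include hypoglycemia and adherence, which can respond to a known schedule. Adherence also decides who enters the primary per-protocol analysis. Second, each insulin arm injects on one schedule while its placebo comparator is a mix of both. If injection frequency itself affects the outcome, through adherence, meal behaviour or contact, part of that effect enters each insulin-versus-placebo contrast.

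**Working it through.** **Inputs.** Planned group size 20 (15 evaluable), SD 4.0 for ΔQP, within-subject correlation 0.6 and 80% power, from section 14; 1:1:1 allocation and the half-and-half placebo split, from section 8.3. Alpha is not stated; two-sided 0.05 is assumed. How the placebo schedules are allocated within strata is also not stated; an even 10/10 split is assumed.

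**1. What the schedule reveals.** Planned layout:

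| Schedule | Basal | Pre-meal | Placebo | Total |
|---|---|---|---|---|
| Once daily | 20 | 0 | 10 | 30 |
| Three times daily | 0 | 20 | 10 | 30 |

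The chance of being on insulin is 20/30 = 67% on either schedule, so frequency carries no information about insulin versus placebo. It excludes one insulin arm with certainty for all 60 participants. Basal and pre-meal recipients never share a schedule.

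**2. Effect of schedule on the contrasts.** Let b and m be the insulin effects of the basal and pre-meal regimens, and s the effect of injecting three times rather than once daily. Relative to once-daily placebo, the expected arm means are basal b, pre-meal m + s, and placebo s/2. Then:

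- basal - placebo = b - s/2
- pre-meal - placebo = m + s/2
- basal - pre-meal = b - m - s
- average of the two insulin arms - placebo = (b + m)/2

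The last line is free of s only if the split is even. If a fraction p of analysed placebo participants is on three injections, the first two shifts become -ps and +(1 - p)s. The documents give no value for s. As an assumed range, s from 0 to 2.0 on the ΔQP scale gives a shift of 0 to 1.0, which is 0 to 30% of the stated detectable difference of 3.3 (1.0/3.3 = 0.30).

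**3. The plan's own detectable differences.** SD of change = 4.0 × √(2 × 0.4) = 3.58, given as 3.6. The two-sample t calculation gives 3.81 for 15 per group and 3.27 for 20, which round to the stated 3.8 and 3.3. These figures reproduce and are not affected by the blinding point.

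**4. Cost of comparing with same-schedule placebo only.** The variance factor is 1/20 + 1/20 = 0.10 as planned and 1/20 + 1/10 = 0.15 for the same-schedule contrast, half as large again. The detectable ΔQP is 4.05 with two-group error degrees of freedom and 3.97 with the error pooled over all arms, so about 4.0 against 3.3. Power at a true difference of 3.3 falls to about 63%. With 15 versus 7 or 8, the detectable ΔQP is 4.85 or 4.63, against 3.8.

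**5. Adding a schedule term to the planned model.** Basal is all once daily and pre-meal all three times daily, so the term can be estimated only from the two placebo halves. Each insulin-versus-placebo contrast goes from 0.10 to 0.15. Basal versus pre-meal becomes (1/20 + 1/10) + (1/20 + 1/10) = 0.30, three times the planned 0.10. For all insulin against all placebo, the adjusted factor 0.25 × (1/20 + 1/10 + 1/20 + 1/10) = 0.075 equals the unadjusted 1/40 + 1/20 = 0.075. But section 14 does not name that contrast, and step 2 shows that an even split already balances it.

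**The case against.** The strongest reply is that the split placebo is there to protect the comparison that most needs masking. It succeeds: schedule alone cannot tell anyone whether they inject insulin or placebo. The primary endpoints in section 14 are isotope-derived and modelled by collaborators blinded to arm, so biased assessment has little room. Subclinical hypoglycemia is identified from the glucose monitor. Injection frequency is also part of what Aim 2 compares, since section 1.1 presents once-daily dosing as the more convenient option. All of this stands. It limits the consequence but does not make section 8.3 accurate.

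Several stronger readings are tempting, and the documents do not support them:

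- **That everyone is unblinded.** Section 16.1 keeps the modelling collaborators blinded to arm.
- **That pooling mixes blinded and unblinded placebo comparisons.** The other-schedule half is schedule-mismatched. Those participants still cannot tell placebo from insulin by frequency.
- **That section 20.1 identifies insulin recipients because it names only the pre-meal insulin arm.** Nothing says that placebo participants on three injections are handled differently at school.
- **That a schedule term should simply be added at no cost.** Step 5 shows that in the planned pairwise model it triples the Aim 2 variance. It would also remove part of the regimen difference that Aim 2 asks about.

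**Conclusion.** The blinding statement is wrong as written for one of the two main treatment aims. Insulin versus placebo is masked within each schedule as far as injection frequency goes. Basal versus pre-meal is open to all 60 CF participants and to the staff who train, adjust or dose them, and not to the metabolic modellers. Each insulin-versus-placebo contrast carries a shift of about half of any schedule effect, in opposite directions for the two regimens. The documents give no basis for the size of that effect, and it may be small for phenylalanine flux.

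The conclusion rests on there being no double-dummy, since none is described, and on a roughly even placebo split. Per-protocol exclusions could disturb that split. The point concerns how the trial is described and one missing sensitivity analysis; it does not show that the primary comparison with placebo is unmasked.

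**What to change.** In sections 1.1, 5.1 and 8.3, and where the purpose paragraph is repeated in 8.5 and 19.2, state that blinding covers insulin versus placebo within injection schedule, and that basal versus pre-meal is open to participants and clinic staff. Report Aim 2 on that basis, including its hypoglycemia and adherence comparisons, and note there that the modelling of the isotope data was blinded to arm.

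In section 14, keep the three-arm pairwise model as primary, without a schedule term. Add a pre-specified sensitivity analysis comparing each regimen with placebo on the same schedule, and report how many analysed placebo participants were on each schedule.

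The cost is wording and one additional analysis. The sensitivity analysis is less precise (variance factor 0.15 against 0.10; detectable ΔQP about 4.0 against 3.3 with 20 per arm), so it should be read for consistency of direction and size with the primary result, not as a separate test. The other cost is that Aim 2 can no longer be presented as double-blind. No change to visits, treatment or sample size is needed.

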insulintherapy. They could also have hypoglycemic reactions during the jello part of the study. This will be closely monitored and they will receive juice if symptoms arise.

2. There is potential for discomfort as the iv is being inserted and at the iv site.

3. The stable isotopes to be infused are naturally occurring isotope of amino acids and thus the amino acids are not anticipated to pose any risk. During preparation of any iv solution there is the potential for contamination which is why the isotopes will be prepared by the investigational pharmacy under their usual sterile protocol.

4. Confidentiality may be breached.

5. Nausea from eating the Jello.

6. DXA is an x-ray that has very little radiation exposure.

7. The continuous glucose monitor may cause some discomfort, inflammation or irritation at the site.

13. Potential Benefits to Participants

13.1. Potential Benefits: It is possible that there is no benefit for participants because they may not receive active drug. There is a possibility that insulin replacement therapy may be effective in breaking the cycle of underweight and overall clinical deterioration because of its potent anabolic effects on protein turnover.

14. Statistical Considerations

This study will compare the three parallel treatment groups (placebo, basal insulin, and pre-meal insulin) on the basis of within-subject changes from week 0 (baseline) to week 8 (after 1 month of assigned treatment). The primary endpoints are within-subject differences from week 0 to week 8 in protein turnover parameters, change in Phe flux (ΔQP) and in conversion of Phe to Tyr (ΔQPT). Treatment groups will be compared by pairwise contrasts in analysis of variance, adjusted for baseline protein turnover. The primary-endpoint analysis will be per-protocol, performed on adherent subjects who received at least 70% of study medication in order to assess insulin effects. In addition, as part of planning for a larger trial, an intent-to-treat analysis will be performed, including all randomized participants to assess insulin treatment effects in practice. Exploratory analyses will examine associations between differences in protein turnover parameters and mechanistic endpoints: baseline pulmonary function, BMI percentile, dietary intake (from diet records), observed plasma glucose mean and MAGE (from CGM), cytokines, and treatment adherence.

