
We anticipate that 45 participants, 15 from each of 3 arms, will provide sufficient power to detect clinically significant improvements in protein turnover (ΔQP and ΔQPT) at baseline, based on comparisons between healthy controls and insulin-insufficient CF patients in our previous study (18). Details are given below. We have inflated the sample size to 20 per arm to allow replacement of drop-outs and non-adherent participants, participants who develop diabetes, or suffer an acute exacerbation. The most common reason for drop out is likely to be acute illness, although the brief (3 month) time span will help reduce this. Also, given the short time span of this study we anticipate adherence will be good. This is in line with other studies in CF where about 80% of subjects are adherent at least 80% of the time (24, 65). Because many of our subjects will be adolescents, one might expect somewhat worse adherence. However, we believe this will be offset by the short duration of the study and by mechanisms to encourage adherence such as school nurse supervision on school days and frequent contact with study personnel. Study drop-out may occur due to development of fasting hyperglycemia or acute illness. These are discussed in greater detail in the human

PROTOCOL TITLE: The Impact of Insulin Therapy on Protein Turnover in Pre-Diabetic Cystic Fibrosis Patients

VERSION DATE: 28 June 2021

subjects section. We expect less than 2% of subjects to develop CFRD during the 3 month study period. Patients who experience acute illness during the study may repeat it when they are well. Thus, we have inflated our group size to account for 20% non-adherence, 1-2% development of diabetes, and 11-12% acute illness.

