Because studies of the effect of chronic insulin therapy have not been conducted previously in CF patients, precise estimates of treatment effect cannot be made. We previously demonstrated significant insulin treatment effects protein on *de novo* synthesis in 14 non-CF study participants, 7 with type 1 diabetes and 7 without (66). Previous work (24) gave estimates for CF patients of the standard deviation (SD) of changes in protein turnover parameters ΔQP and ΔQPT , differences between conditions of insulin infusion and baseline fasting. The primary endpoint is the within-subject change in ΔQP and ΔQPT from week 0 (baseline) to week 8 (after 1 month of assigned treatment), and we estimated the SD of these changes as $(SD \text{ of } \Delta QX) \sqrt{2(1 - \rho)}$, assuming $\rho=.6$ for within-subject correlation, for $\Delta QP = 4.0$ and $\Delta QPT = 1.26$. The table below reports these standard deviations and shows corresponding minimum differences that the study would have 80% power to detect with sample sizes of 15 or 20 in each group. For context, these minimum detectable differences are also given as percent of the baseline value in the CF patients. Observed mean differences in ΔQP and ΔQPT between CF patients and healthy controls were *larger* than the minimum detectable differences for $n = 15/\text{group}$ (24). To the degree that either insulin treatment is able to normalize protein turnover in the CF patients, these observed differences suggest possible treatment effects.

N per group	Minimum detectable	Minimum detectable difference as % of	Observed mean difference (CF patients –
ΔQP (SD = 3.6)		baseline mean = 50.8	6.0
15	3.8	7%	
20	3.3	6%	
ΔQPT (SD =		baseline mean = 6.43	1.5
15	1.2	19%	
20	1.0	16%	

The unblinded study statistician will perform new sample size calculations after the first 15 CF subjects (5 in each group), and, if necessary, additional subjects will be studied.

15. Confidentiality

PROTOCOL TITLE: The Impact of Insulin Therapy on Protein Turnover in Pre-Diabetic Cystic Fibrosis Patients

VERSION DATE: 28 June 2021

15.1. Data Security: The PI, [name], will store and maintain data indefinitely on her password protected UM desktop computer in her locked office which is maintained by the AHC.

16. Provisions to Monitor the Data to Ensure the Safety of Participants

16.1. Data Integrity Monitoring.

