Ideally, both custodial parents or guardians would be present in person at a study visit. However, if one parent is unable to attend a visit in person the signature can be obtained on a remote basis. In general, this is done by providing the study materials (handbook, consent forms) to the parent and then speaking to the second parent by phone to provide fully informed consent.

After discussing the study and answering questions, the signed consent form can be returned (sent via mail, email, or fax) or brought to the study visit by the other responsible parent. If the signature dates are different (which is likely), an explanation that the remote signature was collected off site should be noted in the source document. If, in rare cases, one of the custodial parents is not available despite efforts to reach them (e.g. active duty), this should be documented in a note to file.

19.3 Non-English Speaking Participants: We have a translated parental consent form for those patients that have Spanish speaking parents to abide by our unexpected encounter that we will have used the short form on.

20. Setting

20.1. Research Sites:

- [name] maintains the CF OGTT Database and follows these patients clinically and will identify potential subjects through this.
- Research procedures will take place at the University of Minnesota Health Clinical Research Unit (M Health CRU) as well as at the Delaware Clinical Research Unit (DCRU).
- School-aged participants who are randomized into the pre-meal insulin arm will require the school to assist in the proper storage and overseeing the administration of the required insulin dosage.

21. Multi-Site Research

21.1. Study-Wide Number of Participants: 100-- number is high in case of drop outs, especially due to acute illnesses which are common in CF patients

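### The primary contrasts omit the age-group and gender strata used in randomisation; adding them costs almost nothing and recovers precision if either predicts the change beyond baseline

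*Combined protocol and SAP*

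**What the plan says.** Section 8.3 (Screening) allocates CF subjects 1:1:1, "stratified by 2 age intervals (10-17, 18-25y) and gender". It adds: "Randomization will be done with computer-generated lists for each strata, in randomly alternating blocks of 3 and 6". That makes four strata.

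Section 14 (Statistical Considerations) defines the primary comparison: "Treatment groups will be compared by pairwise contrasts in analysis of variance, adjusted for baseline protein turnover". Baseline turnover is the only covariate named. The primary analysis is per-protocol, "performed on adherent subjects who received at least 70% of study medication". Alongside it, "an intent-to-treat analysis will be performed, including all randomized participants to assess insulin treatment effects in practice".

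Age group and gender appear in neither model, nor in the list of exploratory associations. Section 16.1 asks for similar numbers by gender and age band, but that concerns recruitment, not analysis.

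**The concern.** Stratified allocation balances the arms on age group and gender. If those factors predict the change in turnover, the balance reduces the true sampling variance of each contrast. A model that omits them leaves their variance in the residual, so its standard error is too large and the test is conservative. With about 15 analysed per arm, precision is scarce, and this precision has already been paid for in the randomisation.

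A second reason is specific to this trial. The primary set is selected on adherence, so the balance created at randomisation need not survive into it. The Power Analysis concedes: "Because many of our subjects will be adolescents, one might expect somewhat worse adherence". It then says it expects this to be offset. Section 20.1 states: "School-aged participants who are randomized into the pre-meal insulin arm will require the school to assist in the proper storage". If retention differs by arm and age group together, the arms analysed differ in age mix, and an unadjusted contrast can be shifted as well as less precise.

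**Working it through.** **1. The plan's own figures.** The Power Analysis reports "minimum differences that the study would have 80% power to detect with sample sizes of 15 or 20 in each group". Inputs there: SD 4.0 (ΔQP) and 1.26 (ΔQPT), within-subject correlation 0.6. SD of the change = SD × √(2(1 − 0.6)) = SD × 0.894, giving 3.58 (tabulated as 3.6) and 1.127. No alpha is stated. A two-group t calculation at two-sided 0.05 and 80% power gives:

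- ΔQP: 3.82 (n = 15) and 3.27 (n = 20), against 3.8 and 3.3 stated.
- ΔQPT: 1.19 and 1.02, against 1.2 and 1.0 stated.

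The table is reproduced. One-sided 0.05 (3.35 and 2.88 for ΔQP) and a Bonferroni correction over three contrasts (4.41 and 3.78) do not match it, so two-sided 0.05 per contrast is used below.

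**2. Cost and gain by formula.** With 45 analysed, three arms and one covariate, error df = 45 − 4 = 41; two main effects reduce this to 39. If R² = 0, the minimum detectable ΔQP difference moves only from 3.772 to 3.777. If R² > 0, the residual SD becomes 3.6 × √(1 − R²), and the detectable difference falls to 3.68, 3.58, 3.38 and 3.16 at R² of 0.05, 0.1, 0.2 and 0.3. These gains are upper figures: they assume the analysed arms stay balanced and give the unadjusted analysis no credit for stratification.

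**3. Simulation, which removes both simplifications.** 60 subjects randomised 1:1:1 in four strata with blocks of 3 and 6; 45 analysed; ANCOVA on baseline with or without age group and gender; true difference 3.8/3.6 = 1.06 SD; R² split equally over the two factors; 20,000 trials per setting. SD 3.6 is taken as the SD after baseline adjustment. Ranges cover three loss patterns: random, exactly 15 kept per arm, and random with a 35/65 age mix.

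| R² (assumed) | SE ratio, without/with strata | Power without | Power with | Type I error without |
|---|---|---|---|---|
| 0 | 0.992 | 78.6–79.3% | 78.1–78.7% | 4.8–5.3% |
| 0.02 | 1.002–1.003 | 79.3–80.1% | 79.2–80.2% | 4.7–5.0% |
| 0.05 | 1.019 | 79.5–80.0% | 80.7–80.9% | 4.3–4.7% |
| 0.1 | 1.047–1.048 | 79.8–80.6% | 82.5–83.3% | 4.1–4.2% |
| 0.2 | 1.113 | 80.5–80.8% | 86.4–87.0% | 3.4–3.5% |
| 0.3 | 1.192–1.193 | 80.8–81.6% | 90.2–90.9% | 2.6–2.8% |

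With the strata included, type I error is 4.8–5.2% throughout. A separate simulation shows the mechanism: at R² = 0.2 without strata, the mean model SE is 1.34 against a true sampling SD of 1.26. ΔQPT behaves almost identically, since 1.2/1.127 = 1.06 SD. With all 60 analysed, the SE ratios are 0.999, 1.025, 1.054, 1.121 and 1.200 at R² of 0, 0.05, 0.1, 0.2 and 0.3.

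**4. Retention differing by arm and age.** With equal age groups at randomisation and age the only predictor, the difference between age groups is 2√R² SD, so shift = (adult share − 0.5) × 2√R². Suppose one arm keeps 55% of adolescents and 85% of adults, and the other keeps 80% of both (invented figures). The adult share in the first arm is 0.85/1.40 = 0.607, and the shift is 0.030, 0.048, 0.068 and 0.096 SD at R² of 0.02, 0.05, 0.1 and 0.2, or 0.11 to 0.34 in ΔQP. With milder retention of 70% and 80% in that arm, the share is 0.80/1.50 = 0.533 and the shift is 0.009 to 0.030 SD. Simulation of the 55%/85% case gave 0.030 to 0.103 SD unadjusted and −0.006 to 0.005 SD adjusted.

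**The case against.** **The planned test is valid.** Under ignorable loss its type I error is at or below about 5%, and power stays near 80%. This stands: nothing the protocol claims fails.

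**The gain rests on an unknown R².** The endpoint is a within-subject change already adjusted for baseline, so stable age or gender differences in turnover level are largely removed. This also stands. Between R² of 0 and 0.05 the effect runs from a loss of under one power point to a gain of about one.

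**Starting power may be understated.** The protocol gives 3.6 as the SD of the change, not the SD after baseline adjustment. With SD 4.0, correlation 0.6 and equal variance at both times assumed, the adjusted SD is 4.0 × √(1 − 0.36) = 3.2. Simulated power, without versus with strata, is then 87.9% and 87.0% at R² = 0, 87.5% and 89.6% at 0.1, 89.4% and 93.2% at 0.2, and 89.9% and 95.9% at 0.3. The power gain shrinks to about 2 to 6 points; the SE ratios do not change.

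**The retention scenario is illustrative.** Section 14 counts school nurse supervision as an aid to adherence, half the placebo arm also injects before meals (Section 8.3), and ill patients may repeat the study. All fair. Even so, pre-meal dosing applies to one arm fully, one by half and one not at all, so a difference by arm and age is possible. Its direction and size are unknown. Covariates remove the shift only if loss is random within arm and age group; they do not cure adherence selection in general.

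**The trial is under way.** Section 9.1 reports 40 CF patients consented, Section 16.2 reports 24 subjects studied, and Section 14 gives an unblinded statistician a sample-size recalculation after 15. The change therefore needs a record that it was made without sight of results.

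**Conclusion.** The concern holds, as an improvement and not as a fault that breaks the design. The strata used to randomise are absent from the primary and intent-to-treat models.

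Omitting them makes the standard error about 5% to 19% too wide if age and gender explain 10% to 30% of the baseline-adjusted variance. That is worth about 2 to 9 power points with a residual SD of 3.6, or 2 to 6 with 3.2. At R² of 0.02 to 0.05 the gain is negligible. If R² is zero, including them costs about 0.8% in standard error and less than one power point. The possible loss from adjusting is small and bounded, while the possible gain is several times larger.

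This rests on assumptions the documents do not settle: R², a two-sided 0.05 level per contrast, 45 of 60 analysed, and loss unrelated to arm and stratum. If that last assumption fails, the shift in the examples worked is at most 0.10 SD, or 0.34 in ΔQP against a detectable difference of 3.8: modest, but removable when loss is random within arm and age group.

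**What to change.** In Section 14, state that the comparisons of ΔQP and ΔQPT, per-protocol and intent-to-treat, include age group and gender as main effects alongside baseline turnover. Main effects take two degrees of freedom; a four-level stratum term would take three for little return at this size.

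Code age with the cut used to randomise (10–17, 18–25). Section 16.1 describes different bands (10–18, and a young-adult band printed as 19–15), so name the cut explicitly.

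The cost is one sentence, two degrees of freedom and no new data. If age and gender explain nothing, the standard error rises by about 0.8% with 45 analysed and about 0.1% with all 60. Date the amendment and record that whoever specified it had not seen results by arm; Section 16.2 says efficacy data stay unreviewed until study end, so this should be possible.
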